**Note:** In the UK, serious AEs (SAEs) will be recorded from time of consent through the EoS **or** until the Investigator and Imago BioSciences determine follow-up is no longer necessary.

Physical Examinations (PE), including vital signs: a **Full Physical Exam** will be performed at Screening. **Limited Physical Exams (LPE)** will be performed at all other clinic visits throughout the study. LPEs include weight, a review of body systems to assess change from previous PE, and spleen measurement. The edge of the spleen shall be determined by palpation, measured in centimeters, using a soft ruler/tape, from the costal margin to the point of greatest splenic protrusion. The spleen should be measured in the same manner at all visits.

Urine or serum pregnancy testing will be performed for women of child-bearing potential (WOCBP; defined in Section 6.1 ) at Screening, Baseline (if separate from Screening visit), pre-dose Day 0, monthly (i.e., Days 28, 56, 84, 112, 140 and 168) throughout the study, upon suspicion of relapse, at the EoT, pre-EoS, and EoS/ET visits and if pregnancy is suspected while the patient remains on-study.

Bone marrow aspirate\* and biopsy will be performed\*\*:

- At Baseline (no more than 21 days prior to the first IMG-7289 dose).
- At Day 168 ( $\pm 7$  days).
- Approximately every 6 months thereafter, at Day 168 ( $\pm 7$  days) of the ATP, for as long as the patient continues to qualify.
- At EoT and ET (unless performed within the prior 5 weeks), and upon suspicion of relapse (unless performed in the last 21 days or is scheduled in the next 7 days).

\*Aspirate from the first pull whenever possible, but no later than the second pull, is required.

\*\*The total number of bone marrow evaluations required during the ITP is 2 in ~32 weeks. Additional marrow evaluation is required only if the patient qualifies for the ATP, demonstrates response followed by suspected relapse, or evidence of progressive disease.

MRI or CT (if the patient is not a candidate for MRI) of the abdomen will be performed.

- Pre-dose Day 0 ( $\pm 2$  days)
- At the Day 84 and Day 168 visits ( $\pm 7$  days)
- Approximately every 6 months thereafter, at Day 168 ( $\pm 7$  days) of the ATP, for as long as the patient continues to qualify

- At EoT, ET, and upon suspicion of relapse (unless performed within the prior 5 weeks)

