**Note:** In Germany, use of computerised tomography (CT) is not permitted for patients unable to undergo magnetic resonance imaging (MRI). Only MRI is permitted for study purposes.

Clinical laboratory measures: The following laboratory measures will be performed at Screening, Baseline (if separate from Screening visit), pre-dose Day 0, upon suspicion of relapse, at the EoT, pre-EoS, and EoS/ET visits, and in accordance with the below:

- Biochemistry – monthly (i.e., Days 28, 56, 84, 112, 140 and 168) throughout the study
- Haematology – every clinic visit throughout the study
- Coagulation – monthly (i.e., Days 28, 56, 84, 112, 140 and 168) throughout the study
- Urinalysis – Day 84 and Day 168 throughout the study

CCI [REDACTED] Sample collection time-points are below.

- Pre-dose Day 0, Days 14, 28, 84 and 168, and each Day 168 visit of the ATP, for as long as the patient continues to qualify
- At EoT, and at ET (ET required only if the patient discontinues during the ITP)

Red Cell Haemoglobin F (HbF) and %F cells (Selected sites only/ITP only):

- Pre-dose Day 0, Day 84 and Day 168
- At EoT and ET (both required only if the patient discontinues during the ITP)

CCI [REDACTED]

\*Any bone marrow aspirate samples will undergo genomic analysis as per the bone marrow sampling schedule.

CCI [REDACTED]

Blood, bone marrow and/or their contents may be retained for future exploratory studies.

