### **5.1.1 Initial Treatment Period (ITP)**

Through the use of dose titration, all patients will be dosed to the  $D_{pi}$  of IMG-7289. The  $D_{pi}$  is anticipated to be  $\leq 2$  mg/kg QD; however, this is not the upper limit for titration purposes as the dose needed to achieve a therapeutic effect will vary among patients and may change over time. The platelet titration target expected to be associated with a clinically significant therapeutic effect is:

- A platelet count of  $\geq 50$  to  $\leq 75$  k/ $\mu$ L ( $50-75 \times 10^9/L$ )

Additional details pertaining to dosing are located in Section 7.2.3.

During the ITP, patients will return to the clinic for study assessments weekly for 8 weeks (ITP Days 7, 14, 21, 28, 35, 42, 49 and 56), at least bi-weekly for 8 weeks (ITP Days 70, 84, 98 and 112) and then monthly for 8 weeks (ITP Days 140 and 168). It is anticipated that by Week 8 (Day 56) patients will have achieved a stable dose, with weekly visits no longer necessary. For the exceptional patient whose dose has not stabilized, weekly visits may continue at the PI's discretion (note: bi-weekly visits may also continue post Day 112). On Days 84 and 168, patients will undergo abdominal MRI or CT (if the patient is not a candidate for MRI). On Day 168, bone marrow sampling is also required. Prior to or at the Day 168 visit, but ideally at the Day 140 visit for logistical purposes, a 'qualification' assessment will be made to determine whether the patient is deriving clinical benefit. Such patients qualify for entry into the ATP, a transition which should occur without interruption in dosing. Patients not deriving clinical benefit, or who achieve CR, PR or CI and subsequently relapse (Section 16.7), the equivalent of treatment failures, will discontinue IMG-7289 and undergo all necessary follow up visits.

**Note:** In Germany, use of computerised tomography (CT) is not permitted for patients unable to undergo magnetic resonance imaging (MRI). Only MRI is permitted for study purposes.

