This study initiated as a Phase 1/2a study assessing the safety of the starting dose, an CCI [REDACTED] duration of treatment, and the pharmacokinetic and pharmacodynamic effects of IMG-7289 (under original protocol and amendments 2-4), with transition to a Phase 2b study incorporating changes supported by the Phase 1/2a data (under amendments 4-6).

This study consists of two periods: The Initial Treatment Period, followed by the Additional Treatment Period. In the Additional Treatment Period, which is iterative, treatment may continue in those patients deriving clinical benefit and safely tolerating IMG-7289, as determined by the Principal Investigator.

Patients enrolled in the Phase 1/2a portion of study are treated in the ITP daily for CCI [REDACTED] if qualified, they may continue to the ATP after a brief washout period, and be treated daily for an additional CCI [REDACTED]. Patients enrolled in the Phase 2b portion of study are treated in the ITP daily for CCI [REDACTED]; if qualified, they may continue directly to the ATP with no washout period, and be treated daily for an additional 169 days.

The protocol, IMG-7289-CTP-102, describes the general approach to analysis of data from the study. The purpose of this Statistical Analysis Plan (SAP) is to outline the statistical principles which will be used to analyze and present the

data, including definition of endpoints, stopping rules, and analysis populations.
Table, Figure, and Listing shells will be supplied in an accompanying document.

CCI

CCI

II. Protocol Objectives

The following primary and exploratory objectives will be evaluated in patients with myelofibrosis including primary myelofibrosis (PMF), post-polycythaemia vera-myelofibrosis (PPV-MF), and post-essential thrombocythaemia-myelofibrosis (PET-MF) (collectively referred to as 'MF').

A. Primary

To evaluate in MF patients the effect of IMG-7289 on:

- Safety and tolerability
- Pharmacokinetics (Phase 1/2a only)
- Reduction in spleen volume

CCI

III. Study Endpoints

A. Primary

- The safety and tolerability of IMG-7289 will be assessed by the analysis of adverse events (AEs), as well as changes in physical examinations, vital signs and laboratory values **CCI**

CCI

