Approximately seventy-five (75) MF patients are expected to be enrolled and treated in the study and a minimum of 45 patients are required to complete the entirety of the Initial Treatment Period (including MRI/CT). This study is designed to make an assessment of the safety, tolerability, and pharmacokinetics of the capsule formulation of IMG-7289. The Phase 1/2a portion of the study was planned for a minimum of 15 patients; with 18 enrolled and treated patients, the Phase 1/2a portion of the study is sufficiently powered to determine mean pharmacokinetic parameters. Given that all pharmacodynamic (PD) metrics are exploratory in nature, the study is not powered to make statements about the statistical significance of any changes observed.

D. Treatment Randomization

This is not a randomized study.

CCI

CC

V. Interventions

A. Clinical Trial Material

The drug product is IMG-7289, a bis-tosylate salt. The free base of IMG-7289 is the active moiety. IMG-7289 will be supplied in capsules of multiple strengths. These strengths, based on IMG-7289 free base, i.e. the active substance, may include: 1 mg, 5 mg, 10 mg, 25 mg, and 50 mg. At Phase 2b, 1 mg capsules are not provided.

B. Study Procedures

Patients will undergo procedures described in protocol Section 9 to assess the study drug safety, pharmacodynamics, and pharmacokinetics in order to achieve the study objectives.

VI. General Analytical Considerations

The statistical analyses will be reported using summary tables, figures, and data listings. Unless otherwise noted, all statistical testing will be two-sided with significance being $p < 0.05$. Continuous variables will be summarized with means, standard deviations, medians, minimums, and maximums. Categorical variables will be summarized by counts and by percentage of patients in corresponding categories. As appropriate and where specified, continuous and categorical variables will be evaluated using the paired t-test, Kruskal-Wallis, Wilcoxon rank sum, Sign rank test, Fisher's exact, or χ^2 tests to assess the significance of differences in haematologic, pharmacodynamics markers, and response. As appropriate and where specified, summary tables will be presented by the type of disease within starting dose, with an "All Patients" summary. Refer to section VI.K for details.

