VIII. Efficacy Analyses

A. Primary Analysis

1. Spleen Volume

Spleen volume (mL) will be measured by MRI (or CT scan where applicable) from Day 0. Descriptive statistics will be presented for actual spleen volume, change from baseline, and percentage change from baseline by visit; and for maximum percentage change from baseline, minimum percentage change from baseline, and best percentage change from baseline will be presented. The best percentage change from baseline is defined as the maximum percentage decrease or the minimum percentage increase if there is no decrease in a patient during treatment.

In addition, an analysis of mean spleen volume will be performed. The mean and its 95% confidence interval (CI) will be presented for the spleen volume (mL), change from baseline, and percentage change from baseline at each visit; and for the best percentage change from baseline. P-value for test to assess change from baseline at each visit will be calculated using paired t-test. P-value for test to assess percentage change from baseline at each visit and the best percentage change from baseline will be calculated using one sample t-test with the hypothesis that the percentage change is 0.

2. Spleen Size

Spleen size (cm) will be measured by palpation at each visit. Descriptive statistics will be presented for actual spleen size, change from baseline, and percentage change from baseline by visit; and for maximum percentage change from baseline, minimum percentage change from baseline, and best percentage change from baseline will be presented. The best percentage change from baseline is defined as the maximum percentage decrease or the minimum percentage increase if there is no decrease in a patient during treatment.

In addition, an analysis of mean spleen size will be performed. The mean and its 95% confidence interval (CI) will be presented for the spleen size (cm), change from baseline, and percentage change from baseline at each visit; and for the best percentage change from baseline. P-value for test to assess change from baseline at each visit will be calculated using paired t-test. P-value for test to assess percentage change from baseline at each visit and the best percentage change from baseline will be calculated using one sample t-test with the hypothesis that the percentage change is 0.

CCI

CCI

CCI

CCI

CCI

[figure not shown]

IX. Safety Analyses

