Sites are intended to document on the AE eCRF those events with an onset date on or after the date on which IMG-7289 was first dispensed, and within 28 days of last IMG-7289 treatment; therefore, all reported AEs are expected to be treatment-emergent. However, if eCRF completion guidelines change, or are not followed adequately, treatment-emergent events will be identified programmatically per the above definition, using imputed start date.

CCI

C. Clinical Laboratory Results

The following laboratory tests will be conducted:

- Complete blood counts (CBC) and differential
- Coagulation
- Chemistry panel including LFTs (AST, ALT, total bilirubin and alkaline phosphatase (ALP)) gamma glutamyltransferase (GGT), albumin , C-reactive protein), lactate dehydrogenase (LDH), uric acid. *Note that C-reactive protein was added starting with amendment 5.*
- Urinalysis with microscopy

Laboratory values will be listed and summarized at each assessment. Numerical laboratory results will be summarized for the actual values, change from baseline (CFB), and percentage CFB by visit; and for the maximum and minimum change from baseline. P-value for test to assess maximum and minimum change from baseline within each cohort will be calculated using paired t-test.

Shift tables for laboratory values with respect to normal range (low, normal, high) and CTCAE toxicity grade, compared to baseline, will be summarized by visit. Overall laboratory result shift from baseline (Normal, Abnormal clinically significant (CS), and Abnormal non-clinically significant (NSC)) will be summarized.

D. Vital Signs

Vital sign assessments will be summarized for the actual values, change from baseline, and percentage change from baseline by visit; and for the maximum and minimum change from baseline. P-value for test to assess maximum and minimum change from baseline within each cohort will be calculated using paired t-test.

E. Physical Examination

Physical exam data will be listed. Note that for Phase 2b patients, a limited version of physical exam data is collected.

F. Prior and Concomitant Medications

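### The SAP tests each patient's best spleen change, and the extreme laboratory and vital-sign changes, against zero, so with two or more post-baseline values the 0.05 level does not hold

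*SAP*

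**What the plan says.** SAP II.A lists "Reduction in spleen volume" among the primary objectives. Under Primary Analysis, SAP VIII.A.1 (volume) and VIII.A.2 (palpated size) introduce the best percentage change, "defined as the maximum percentage decrease or the minimum percentage increase if there is no decrease in a patient during treatment". This is the smallest signed change that the patient has on treatment. Its mean is reported with a 95% confidence interval and a p-value: "the best percentage change from baseline will be calculated using one sample t-test with the hypothesis that the percentage change is 0". By-visit means, intervals and tests are given in the same paragraphs.

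For laboratory values and vital signs, SAP IX.C and IX.D state: "P-value for test to assess maximum and minimum change from baseline within each cohort will be calculated using paired t-test". SAP VI sets the level: "all statistical testing will be two-sided with significance being" p < 0.05.

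Several post-baseline values per patient are planned in Phase 2b:

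- **Spleen scans:** the protocol synopsis schedules imaging "At the Day 84 and Day 168 visits", with one more scan at the end of each Additional Treatment Period (ATP) cycle.
- **Visits:** protocol 5.1.1 schedules Initial Treatment Period (ITP) visits "weekly for 8 weeks (ITP Days 7, 14, 21, 28, 35, 42, 49 and 56), at least bi-weekly for 8 weeks", then two monthly visits. That is 8 + 4 + 2 = 14 after Day 0, each with haematology, vital signs and palpation.
- **Biochemistry and coagulation:** "monthly (i.e., Days 28, 56, 84, 112, 140 and 168) throughout the study", so six ITP values.

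**The concern.** A test of mean change against zero keeps its level when the value tested is fixed in advance. Here it is chosen after the fact because it is the most favourable. If a patient's changes all have mean zero and are not identical, the smallest of them has a mean below zero. The hypothesis tested is then false without any treatment effect, and the test rejects more often than 5%.

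For the spleen, nearly all the excess points towards an apparent decrease. For laboratory values and vital signs it runs both ways: the maximum can look significantly raised and the minimum significantly lowered for the same parameter with nothing happening.

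At stake is a favourable p-value in the primary spleen table that selection alone could produce, in a single-arm study with no control group to show it up. This is not the multiplicity that SAP VI.I leaves uncontrolled; each of these p-values is wrong on its own.

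**Working it through.** **Inputs from the documents.** Two-sided level 0.05 (SAP VI). Two ITP scans in Phase 2b, three with one ATP cycle. Six or 14 ITP laboratory or vital-sign values. About 75 patients, at least 45 of them ITP completers with imaging, and 18 treated in Phase 1/2a (SAP IV.C).

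**Assumed inputs.** The documents give no SD, between-visit correlation (ρ) or measurement CV, so these are varied. Let every change share one baseline, with measurement-error SD 1 at baseline and follow-up and stable between-patient change of SD d. Then ρ = (d² + 1)/(d² + 2). With no between-patient change (d = 0), ρ = 0.50; with d = 4.24, ρ = 19/20 = 0.95.

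**The plan's own figure.** With one post-baseline value nothing is selected, and simulation returns about 0.05, as intended.

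**Two scans.** For two normal changes with mean 0, SD 1 and correlation ρ:

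- mean of the minimum = −√((1 − ρ)/π)
- variance of the minimum = 1 − (1 − ρ)/π
- noncentrality of the t-test = √n × |mean| / SD

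Example, n = 45, ρ = 0.50: mean −0.399, SD 0.917, noncentrality 6.708 × 0.435 = 2.92. Against a critical value of 2.015 this gives a rejection rate of 0.81.

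Example, n = 45, ρ = 0.95: mean −0.126, SD 0.992, noncentrality 0.853, rejection rate 0.13.

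Rejection rate at nominal 0.05 with no mean change at either scan:

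| n | ρ = 0.50 | 0.80 | 0.90 | 0.95 | 0.98 | 0.99 |
|---|---|---|---|---|---|---|
| 18 | 0.41 | 0.18 | 0.11 | 0.08 | 0.06 | 0.056 |
| 45 | 0.81 | 0.40 | 0.22 | 0.13 | 0.08 | 0.066 |
| 75 | 0.96 | 0.61 | 0.34 | 0.19 | 0.11 | 0.077 |

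The formula treats the minimum as normal; simulation agrees (0.82 and 0.13 for n = 45 at ρ = 0.50 and 0.95). The n = 18 row is an illustrative small group, not the Phase 1/2a patients.

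**Mixed numbers of scans.** Suppose all 18 Phase 1/2a patients complete with one scan, and the other 45 − 18 = 27 completers have two. Simulated rejection is about 37% at ρ = 0.50, 8% at 0.95 and 6% at 0.98. If those 27 also have one ATP scan, it is about 67% at 0.50 and 11–12% at 0.95.

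**Percentage scale, as the SAP tests it.** With no true change and measurement CV from 3% to 20%:

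- 45 patients with two scans: rejection falls from 79% to 55%, and the mean best change goes from −1.6% to −7.6%.
- The 27 + 18 mix: rejection falls from 32% to 13%, and the mean best change goes from −0.9% to −2.9%.
- Between-patient change added so that ρ is about 0.95, CV 3% to 10%: 13% to 12% for the 45, and 8% to 7% for the mix.

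**Laboratory values and vital signs, n = 45 (assumed).** Over ρ = 0.50 to 0.95, six values give 100% to 47% and 14 values give 100% to 72%. SAP VI.C carries the last value forward, which repeats readings. If 40% of patients (30 of 75, the most that 45 completers allow) stop at a random visit, the rates are 100% to 34% and 100% to 60%. With n = 20 and the same stopping they are 93% to 16% and 100% to 31%.

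No rate is given for palpated size, because percentage change is undefined at a 0 cm baseline.

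**The case against.** **The test is valid for its literal hypothesis.** If the hypothesis is that the mean best change is zero, the t-test is sound apart from the usual normality caveat, and the interval properly describes the mean best value. This stands for the interval: it can stay with a footnote. It does not rescue the p-value, because rejecting a hypothesis that is false without any drug effect tells the reader nothing.

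**The inflation may be small.** A correlation of 0.50 means no between-patient variation in true change, which is an extreme case. A CV of 3% with stable between-patient change of SD 20% gives a correlation of about 0.98, where rejection is 8% at n = 45 and 6% at n = 18. SAP VI.L splits results by starting dose and disease type, so many cells may be small: at n = 6 to 10 and correlation 0.95, rejection is 5.4% to 6.6%. This stands as a limit on size. The rate returns to 5% only when the changes are identical.

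**Little depends on these p-values.** No visible decision rule uses them, valid by-visit results sit beside them, and both documents disclaim power for significance statements because pharmacodynamic measures are exploratory. Protocol 12.7 counts spleen volume among those measures. The spurious shift is small beside the 35% volume reduction that defines spleen response in protocol 16.7. In the safety tables the error over-flags changes rather than hiding them. All this holds and limits the severity. But the disclaimer concerns power and does not correct the level, and the SAP still orders the p-values under Primary Analysis.

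**Unseen text.** A caveat could sit in redacted text or in the separate table shells. That cannot be checked.

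**Conclusion.** The concern holds. The tests of best spleen change and of extreme laboratory and vital-sign changes do not have the stated 0.05 level whenever patients have two or more non-identical post-baseline values, which is the planned situation in Phase 2b.

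The direction needs no assumption. For spleen volume, plausible sizes run from about 6% (very high correlation, or one-scan patients mixed in) to about 80% (45 patients with two scans each and no between-patient variation in true change). The laboratory and vital-sign tests are worse because more values are searched. All rates rest on assumed correlations, CVs and group sizes. For platelets, no change is not a realistic null in any case, since titration aims at a lower count. Patients with one post-baseline value add no selection bias, and the by-visit tests select nothing.

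This should be fixed, but it does not threaten the study's main safety conclusions, which also rest on adverse events, by-visit summaries and shift tables.

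**What to change.** **SAP VIII.A.1 and VIII.A.2.** Remove best percentage change from the p-value sentence and from the confidence-interval sentence, and add: *Best percentage change is summarised descriptively, without a p-value or confidence interval; as a selected value it is expected to lie below 0 under no change when a patient has two or more post-baseline values.* If the interval is kept, footnote that it must not be read against 0. A waterfall plot is an option.

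**SAP IX.C and IX.D.** Replace the p-value sentence with: *Maximum and minimum change from baseline are summarised descriptively within each cohort; no p-value is calculated.*

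**Spleen inference.** Rely on the planned by-visit tests, preferably the paired t-test of absolute change, which rejected 4.6% to 5.1% in the no-change simulations. The by-visit percentage test is less safe when measurement is noisy: at n = 75 it rejected 5%, 9% and 19% at CV 3%, 10% and 20%. There the noisy baseline pushes the mean percentage change upward, against the drug.

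**Cost.** SAP wording and a few table shells; no new data. The sponsor gives up a p-value that would have looked favourable.
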